### Thrombocytopenia

Platelet Count	Arm A (standard enoxaparin)	Arm B (adjusted dose enoxaparin)
$\leq 100,000/\mu\text{l}$ and $\geq 50,000/\mu\text{l}$ (CTCAE Grade 1 or 2)	No change	DECREASE to 40mg daily
$< 50,000/\mu\text{l}$ (CTCAE Grade 3 or 4)	HOLD	HOLD

Platelet count will be monitored at least weekly and as part of routine medical care. At any point the platelet count is  $< 50,000/\mu\text{l}$ , then enoxaparin must be held. Enoxaparin should be resumed at when the platelet count is above  $50,000/\mu\text{l}$ . If heparin induced thrombocytopenia is diagnosed then enoxaparin is to be discontinued.

### Hemorrhage

Hemorrhage	Management/Next Dose for  Arm A (standard enoxaparin)	Management/Next Dose for  Arm B (adjusted dose enoxaparin)
$\leq$ Grade 1	No change in dose	No change in dose
Grade 2	Hold* until $\leq$ Grade 1. Resume at same dose.	Hold* until $\leq$ Grade 1. Resume at same dose level.
Grade 3	Discontinue (off protocol therapy)	Discontinue (off protocol therapy)
Grade 4	Discontinue (off protocol therapy)	Discontinue (off protocol therapy)

\*Participants requiring a delay of  $> 3$  days should go off protocol therapy.

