#### **5.6 Criteria for Taking a Participant Off Protocol Therapy**

Cessation of enoxaparin and withdrawal from the study is mandated for the following reasons:

- Grade 3 or 4 hemorrhage and/or
  - Symptomatic hemorrhage in a critical area or organ such as intracranial, intraspinal, intraocular, retroperitoneal, intra-articular or pericardial, or intramuscular with compartment syndrome, and/or hemorrhage causing an acute fall in hemoglobin  $\geq 2\text{g/L}$  or hemorrhage leading to a transfusion of  $\geq 2$  units of packed red blood cells.
- Development of confirmed heparin induced thrombocytopenia
- Proximal deep vein thrombosis or pulmonary embolism
- Condition requiring therapeutic anticoagulation or dual antiplatelet therapy
- Renal failure (see section 6)
- Participant decides to withdraw from the protocol therapy
- General or specific changes in the participant's condition render the participant unacceptable for further treatment in the judgment of the treating investigator

Participants will be removed from the protocol therapy when any of these criteria apply. The reason for removal from protocol therapy, and the date the participant was removed, must be documented in the case report form (CRF). Alternative care options will be discussed with the participant.

A QACT Treatment Ended/Off Study Form will be filled out when a participant is removed from protocol therapy. This form can be found on the QACT website or obtained from the QACT registration staff.

In the event of unusual or life-threatening complications, treating investigators must immediately notify the Overall PI:

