## **6. DOSING DELAYS/DOSE MODIFICATIONS**

Dose delays and modifications will be made as indicated in the following table(s). The descriptions and grading scales found in the revised NCI Common Terminology Criteria for Adverse Events (CTCAE) version 4.0 will be utilized for dose delays and dose modifications. A copy of the CTCAE version 4.0 can be downloaded from the CTEP website [http://ctep.cancer.gov/protocolDevelopment/electronic\\_applications/ctc.htm](http://ctep.cancer.gov/protocolDevelopment/electronic_applications/ctc.htm).

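### The section 6 hemorrhage dosing table is keyed to CTCAE grade alone and omits three of the four bleeding stop criteria in section 5.6

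*Combined protocol and SAP*

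**What the plan says.** Section 5.6 introduces its list with "Cessation of enoxaparin and withdrawal from the study is mandated for the following reasons". The bleeding entry opens with "Grade 3 or 4 hemorrhage and/or" and goes on to symptomatic bleeding in a critical area or organ, then "hemorrhage causing an acute fall in hemoglobin" of at least 2 g/L, or transfusion of at least 2 units of packed red cells. The section closes the list with "Participants will be removed from the protocol therapy when any of these criteria apply". Its only pointer to section 6 is on the renal failure line.

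Section 6 opens by stating that delays and modifications will follow its tables. The hemorrhage table has four grade rows and a column for each arm:

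- Grade 1 or lower: dose unchanged.
- Grade 2: hold until grade 1 or lower, then restart. The Arm B cell says "Resume at same dose level", and Arm A says the same in slightly shorter words.
- Grades 3 and 4: discontinue.

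A footnote takes a participant off protocol therapy if the delay exceeds 3 days. The table does not mention bleeding site, hemoglobin fall or transfusion, and nothing in section 6 refers back to section 5.6.

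**The concern.** Two operative instructions cover the same event and can give opposite answers. Section 5.2.2 says enoxaparin is ordered daily, so a table headed as next-dose management may well be what a clinician consults when writing the order. For a low-graded bleed that meets a grade-independent trigger, the table says to continue, or to hold and restart, while section 5.6 says to stop.

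The bleeds concerned are not trivial in the trial's own terms. The three omitted triggers closely match three of the four criteria for major hemorrhage in section 11, and major hemorrhage is a primary endpoint in both arms. The table could therefore permit re-dosing after an event the trial would itself count as major. In Arm B that means up to 100 mg daily, against 40 mg in Arm A.

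The stake is participant safety and consistent conduct between the two sites. The definitions and the analysis of the primary endpoints do not depend on this table.

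**Working it through.** The plan states no figure to reproduce on this point; the check is a comparison of the two texts.

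**Step 1: are the section 5.6 triggers independent of grade?** The first is joined to the rest by and/or, and removal follows when any criterion is met. Each of the four is therefore sufficient alone, and only the first mentions grade.

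**Step 2: which triggers does the table carry?**

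| Section 5.6 trigger | In the section 6 hemorrhage table? |
|---|---|
| Grade 3 or 4 | Yes (discontinue, both arms) |
| Symptomatic critical-site bleed | No |
| Hemoglobin fall | No |
| Transfusion of 2 or more units | No |

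Four triggers, one carried: 4 − 1 = 3 omitted.

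**Step 3: what does each section direct for a bleed that meets an omitted trigger?**

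| Bleed | Section 6 table | Section 5.6 | Agree? |
|---|---|---|---|
| Grade 1 or lower | No change | Stop | No |
| Grade 2, settles within 3 days | Hold, then restart | Stop | No |
| Grade 2, delay over 3 days | Off therapy | Stop | Yes |
| Grade 3 or 4 | Off therapy | Stop | Yes |

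The result is the same in both arms.

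**Step 4: does section 6 leave off-therapy rules to section 5.6?** Not consistently. The hemorrhage table prints the grade 3–4 stop. The thrombocytopenia part restates the stop for heparin-induced thrombocytopenia, which section 5.6 lists as "Development of confirmed heparin induced thrombocytopenia". The hemorrhage part has no matching sentence for its three grade-independent triggers.

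**Step 5: extra doses in one such case (illustration only).** Further doses allowed by the table = L − d − h, where L is course length in days, d the day of the last dose before the bleed, and h the doses held. The planned course is up to 14 days; 7 days is an assumption, taken from the median in the medical-patient enoxaparin trial described in section 2.2. With d = 4 (assumed):

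- No-change row (h = 0): 7 − 4 − 0 = 3 doses, or 14 − 4 − 0 = 10.
- Grade 2 row, h = 1: 7 − 4 − 1 = 2, or 14 − 4 − 1 = 9.
- Grade 2 row, h = 3: 7 − 4 − 3 = 0, or 14 − 4 − 3 = 7.

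Section 5.6 allows 0 in every case. These figures show the size of the discrepancy for one participant; they do not estimate harm.

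**Step 6: the hemoglobin unit.** Sections 5.6 and 11 both print the threshold as 2 g/L. Dividing by 10 gives 0.2 g/dL, an implausibly small fall to sit beside a 2-unit transfusion as a mandatory stop.

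**The case against.** The strongest reply is that the protocol already requires the right action. Section 5.6 is mandatory and applies when any criterion is met, so required conduct is the same with or without a new row. Section 6 concerns delays and modifications and does not claim to be a complete stop list. Other section 5.6 stops, such as proximal deep vein thrombosis or the participant's own withdrawal, are not repeated there either. This part stands to the extent that there is no missing stop rule and no unresolvable conflict. It does not excuse the table, which gives an explicit instruction for these bleeds, and the wrong one.

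The second reply is that the conflict may never arise. It needs a bleed graded 2 or lower that also meets a severe-sounding trigger, and CTCAE version 4.0 is cited but not reproduced. The hemoglobin route may also narrow sharply if the printed unit is a misprint. Both points stand: frequency is unknown and could be zero. Still, section 5.6 lists the three triggers separately from grade, which would be redundant if grade 3–4 already covered every such bleed.

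There are real safeguards as well: the investigator's right to stop, the requirement that a grade 2 bleed improve before restart, the 3-day limit and a fresh order for each dose. They reduce the risk. None of them covers the no-change row except the investigator's judgment and the daily order.

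**Conclusion.** The concern holds, as a minor safety-consistency point. The table omits three of the four section 5.6 bleeding triggers. In both arms it directs further dosing for a bleed of grade 1 or lower, or a grade 2 bleed settling within 3 days, that meets one of them. Section 5.6 is the controlling text, so the fault is an inconsistent dosing table.

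The conclusion rests on the wording alone and is conditional on such a bleed occurring. It makes no claim about frequency, which the documents do not allow anyone to calculate. The primary estimates are unaffected.

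**What to change.** Add one row to the section 6 hemorrhage table, applying to both arms: *any hemorrhage meeting a section 5.6 criterion, whatever its CTCAE grade, means discontinuation and removal from protocol therapy*. State that this row overrides the grade rows.

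In the same amendment, check the 2 g/L hemoglobin threshold in sections 5.6 and 11 against the published definition that section 11 cites, and correct the unit if needed, so that trivial falls do not trigger the new row.

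The cost is one row, one sentence and one unit check, with no added visits, tests or participants. Some participants with lower-graded bleeds would lose their remaining doses, but only where section 5.6 already requires it. If CTCAE grading turns out to place every such bleed at grade 3 or above, the row serves simply as a cross-reference.

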## Planned Procedures

Enoxaparin may be held for procedures and should be resumed at the discretion of treating physicians.

## 7. ADVERSE EVENTS: LIST AND REPORTING REQUIREMENTS

Adverse event (AE) monitoring and reporting is a routine part of every clinical trial. The following list of reported and/or potential AEs (Section 7.1) and the characteristics of an observed AE (Section 7.2) will determine whether the event requires expedited reporting **in addition** to routine reporting.

### 7.1 Definitions

#### Adverse Event (AE)

An adverse event (AE) is any undesirable sign, symptom or medical condition or experience that develops or worsens in severity after starting the first dose of study treatment or any procedure specified in the protocol, even if the event is not considered to be related to the study. All related adverse events will be followed until resolution.

Abnormal laboratory values or diagnostic test results constitute adverse events only if they induce clinical signs or symptoms or require treatment or further diagnostic tests.

#### Serious adverse event (SAE)

A serious adverse event (SAE) is any adverse event, occurring at any dose and regardless of causality that:

- Results in death
- Is life-threatening. Life-threatening means that the person was at immediate risk of death from the reaction as it occurred, i.e., it does not include a reaction which hypothetically might have caused death had it occurred in a more severe form.
- Prolongs inpatient hospitalization (i.e prolonged a hospitalization beyond the expected length of stay).
- Results in persistent or significant disability/incapacity. Disability is defined as a substantial disruption of a person's ability to conduct normal life functions.
- Is a congenital anomaly or birth defect; or
- Is an important medical event when, based upon appropriate medical judgment, it may jeopardize the participant and require medical or surgical

intervention to prevent one of the outcomes listed above. Examples of such medical events include allergic bronchospasm requiring intensive treatment in an emergency room or at home; blood dyscrasias or convulsions that do not result in inpatient hospitalization, or the development of drug dependency or drug abuse.

Events **not** considered to be serious adverse events are hospitalizations for: routine treatment or monitoring of the studied indication, not associated with any deterioration in condition, or for elective procedures elective or pre-planned treatment for a pre-existing condition that did not worsen. Emergency outpatient treatment for an event not fulfilling the serious criteria outlined above and not resulting in inpatient admission respite care.

### Expectedness

Adverse events can be 'Expected' or 'Unexpected.'

#### Expected adverse event

Expected adverse events are those that have been previously identified as resulting from administration of the agent. For the purposes of this study, an adverse event is considered expected when it appears in the current adverse event list or is included in the informed consent document as a potential risk.

Refer to Section 6.1 for a listing of expected adverse events associated with the study agent(s).

#### Unexpected adverse event

For the purposes of this study, an adverse event is considered unexpected when it varies in nature, intensity or frequency from information provided in the current adverse event list or when it is not included in the informed consent document as a potential risk.

## 7.2 Expected Toxicities

### 7.2.1 Adverse Events List for enoxaparin

Enoxaparin can be associated with an increased risk of hemorrhage including life threatening retroperitoneal, gastrointestinal, or intracranial hemorrhages. Cases of epidural or spinal hematomas have been reported with the associated use of enoxaparin and spinal/epidural anesthesia or spinal puncture resulting in long-term or permanent paralysis. The risk of these events is higher with the use of post-operative indwelling epidural catheters or by the concomitant use of additional drugs affecting hemostasis such as NSAIDs. The rate of major bleeding episodes following enoxaparin (40mg daily) in medical patients with severely restricted mobility during

acute illness was <1%.

Thrombocytopenia can occur with the administration of enoxaparin. Moderate thrombocytopenia (platelet counts between 100,000/mm^3 and 50,000/mm^3) occurred at a rate of 1.3% in patients given enoxaparin, 1.2% in patients given heparin, and 0.7% in patients given placebo in clinical trials. Platelet counts less than 50,000/mm^3 occurred at a rate of 0.1% in patients given enoxaparin, in 0.2% of patients given heparin, and 0.4% of patients given placebo in the same trials. Thrombocytopenia of any degree should be monitored closely. Cases of heparin-induced thrombocytopenia with thrombosis have also been observed in clinical practice. Some of these cases were complicated by organ infarction, limb ischemia, or death.

Asymptomatic increases in aspartate (AST [SGOT]) and alanine (ALT [SGPT]) aminotransferase levels greater than three times the upper limit of normal of the laboratory reference range have been reported in up to 6.1% and 5.9% of patients, respectively, during treatment with enoxaparin. Similar significant increases in aminotransferase levels have also been observed in patients and healthy volunteers treated with heparin and other low molecular weight heparins. Such elevations are fully reversible and are rarely associated with increases in bilirubin.

Mild local irritation, pain, hematoma, ecchymosis, and erythema may follow subcutaneous injection of enoxaparin.

### 7.3 Adverse Event Characteristics

- **CTCAE term (AE description) and grade:** The descriptions and grading scales found in the revised NCI Common Terminology Criteria for Adverse Events (CTCAE) version 4.0 will be utilized for AE reporting. All appropriate treatment areas should have access to a copy of the CTCAE version 4.0. A copy of the CTCAE version 4.0 can be downloaded from the CTEP web site  
[http://ctep.cancer.gov/protocolDevelopment/electronic\\_applications/ctc.htm](http://ctep.cancer.gov/protocolDevelopment/electronic_applications/ctc.htm).
- **For expedited reporting purposes only:**
  - AEs for the agent(s) that are listed above should be reported only if the adverse event varies in nature, intensity or frequency from the expected toxicity information which is provided.
  - Other AEs for the protocol that do not require expedited reporting are outlined in the next section (Expedited Adverse Event Reporting) under the sub-heading of Protocol-Specific Expedited Adverse Event Reporting Exclusions.
- **Attribution of the AE:**
  - Definite – The AE is *clearly related* to the study treatment.
  - Probable – The AE is *likely related* to the study treatment.
  - Possible – The AE *may be related* to the study treatment.
  - Unlikely – The AE is *doubtfully related* to the study treatment.

- Unrelated – The AE is *clearly NOT related* to the study treatment.

## 7.4 Expedited Adverse Event Reporting

7.4.1 Investigators **must** report to the Overall PI any serious adverse event (SAE) attributed to heparin (definite, probable or possible) that occurs after the initial dose of study treatment, during treatment, or within 30 days of the last dose of treatment on the local institutional SAE form.

7.4.2 For multi-institution studies where a DF/HCC investigator is serving as the Overall Principal Investigator, each participating institution **must** abide by the reporting requirements set by the DF/HCC as defined below. This applies to any medical event equivalent to an unexpected grade 2 or 3 with a possible, probable or definite attribution, unexpected grade 4 toxicities, and grade 5 (death) regardless of study phase or attribution.

### 7.4.3 DF/HCC Expedited Reporting Guidelines

Investigative sites within DF/HCC and DF/PCC will report SAEs directly to the DFCI Office for Human Research Studies (OHRs) per the DFCI IRB reporting policy.

Other investigative sites will report SAEs to their respective IRB according to the local IRB's policies and procedures in reporting adverse events. A copy of the submitted institutional SAE form should be forwarded to the Overall PI within the timeframes detailed in the table below.

Attribution	DF/HCC Reportable AEs				
	Gr. 2 & 3 AE Expected	Gr. 2 & 3 AE Unexpected	Gr. 4 AE Expected	Gr. 4 AE Unexpected	Gr. 5 AE Expected or Unexpected
Unrelated Unlikely	Not required	Not required	Not required	5 calendar days b	24 hours a
Possible Probable Definite	Not required	5 calendar days	5 calendar days #	5 calendar days	24 hours a
# If listed in protocol as expected and not requiring expedited reporting, event does not need to be reported.					
a For participants enrolled and actively participating in the study or for AEs occurring within 30 days of the last intervention, the AE should be reported within 24 business hours of learning of the event.					
b Events that are due to underlying malignancy or its treatment do not need to be reported as SAE					

The Overall PI will submit SAE reports from outside institutions to the DFCI OHRs according to DFCI IRB policies and procedures in reporting adverse events.

## 7.5 Reporting to NHLBI

Adverse events and unanticipated problems will be reported by Dr. to NHLBI under the

following timelines:

- Within 7 calendar days of initial receipt of information for fatal or life-threatening unexpected, related serious adverse events.
- Within 15 calendar days of initial receipt of information for non-life threatening unexpected, related SAE
- Within 14 days of the investigator becoming aware of an unanticipated problem that is not an SAE

## **7.6 Expedited Reporting to Hospital Risk Management**

Participating investigators will report to their local Risk Management office any participant safety reports or sentinel events that require reporting according to institutional policy.

## **7.7 Routine Adverse Event Reporting**

All Adverse Events **must** be reported in routine study data submissions to the Overall PI on the toxicity case report forms. **Because of the established toxicity profile of enoxaparin, only attributable AE will need to be recorded. AEs reported through expedited processes (e.g., reported to the IRB, FDA, etc.) must also be reported in routine study data submissions.**

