### **Major hemorrhage:**

An independent adjudication committee of three hematologists will review all details of hemorrhagic events in a blinded manner to determine whether event met criteria for major hemorrhage. Any disagreements will be settled by majority consensus.

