### **12.2 Data Safety Monitoring**

The DF/HCC Data and Safety Monitoring Board (DSMB) will review and monitor study progress, toxicity, safety and other data from this study. The board is chaired by a medical oncologist from outside of DF/HCC and has external and internal representation. Information that raises any questions about participant safety or protocol performance will be addressed by the Overall PI, statistician and study team. Should any major concerns arise, the DSMB will offer recommendations regarding whether or not to suspend the study.

The DSMB will meet twice a year to review accrual, toxicity, response and reporting information. Information to be provided to the DSMB may include: participant accrual; treatment regimen information; adverse events and serious adverse events reported by category; summary of any deaths on study; audit results; and a summary provided by the study team. Other information (e.g. scans, laboratory values) will be provided upon request.

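### Section 7.7 requires all adverse events to be reported but only attributable ones to be recorded, so a non-fatal bleed judged unrelated has no required route onto the toxicity form

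*Combined protocol and SAP*

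**What the plan says.** Section 7.7 contains three statements. The first is general: "All Adverse Events must be reported in routine study data submissions to the Overall PI on the toxicity case report forms". The second narrows it: "Because of the established toxicity profile of enoxaparin, only attributable AE will need to be recorded". The third adds back anything that went through an expedited route, which "must also be reported in routine study data submissions".

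Section 7.1 defines an adverse event without regard to cause, "even if the event is not considered to be related to the study".

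Section 7.4.1 has investigators report to the Overall PI "any serious adverse event (SAE) attributed to heparin (definite, probable or possible"). In the expedited table of 7.4.3, unrelated or unlikely events need no report at grade 2 or 3, or at grade 4 when expected. Grade 5 events are reported whatever the attribution. Footnote b to that table releases events due to the cancer or its treatment from SAE reporting. Section 7.2.1 lists hemorrhage, including life-threatening hemorrhage, among the expected toxicities.

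Section 12.2 says that the DSMB's information may include "adverse events and serious adverse events reported by category". Section 13.4 calls for a DSMB safety analysis whenever hemorrhages on Arm B exceed those on Arm A by more than 2.

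For the endpoint itself, section 11 provides a committee of three hematologists who "will review all details of hemorrhagic events in a blinded manner".

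**The concern.** Two sites could follow different sentences of 7.7 and both comply. One would enter every bleed on the toxicity form; the other would leave out any bleed that the investigator put down to the tumour, recent surgery or chemotherapy. Whether a bleed appears in the adverse-event tables would then depend on an individual causal judgement, which a randomized, blinded comparison is meant to make unnecessary.

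This matters more here than in most trials of an established drug. Estimating major hemorrhage is a primary objective (1.2), and the rationale (2.3) singles out a bleeding estimate for intermediate-dose enoxaparin. Section 2.1 says that the toxicity and appropriate dosing of routine thromboprophylaxis in cancer patients are not known, which sits poorly with an appeal to an established toxicity profile as the reason for recording less.

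**Working it through.** **1. Trace a bleed judged unrelated or unlikely through the adverse-event rules.**

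| Bleed | 7.4.1 (to Overall PI) | Expedited table, 7.4.3 | 7.7 under the attributable-only sentence |
|---|---|---|---|
| Grade 1 | not attributed, so not required | not covered | not recorded |
| Grade 2 or 3 | not required | not required | not recorded |
| Grade 4, expected | not required | not required | not recorded |
| Grade 4, unexpected | not required | 5 calendar days, unless due to the cancer or its treatment (footnote b) | recorded only if expedited |
| Grade 5 | not required | 24 hours, any attribution | recorded, through the expedited route |

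Since hemorrhage is a listed toxicity, a grade 4 bleed will normally fall in the expected row. Among the adverse-event routes, only the fatal case is fully closed.

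**2. Trace the same bleed through the routes that do not use attribution.**

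- Scheduled assessments: the study calendar (section 10) has signs and symptoms of bleeding, not only major bleeding, assessed at screening, day 7 and day 14. Day 7 is not mandatory after discharge. Day 14 still applies, and its symptom assessment can be done by phone (5.2.3).
- Off-therapy record: 5.6 takes a participant off enoxaparin for a grade 3 or 4 bleed and for bleeds on criteria close to the major-hemorrhage definition in section 11. The reason and date must go in the case report form. Cause is not a condition.
- Adjudication: section 11 has no attribution criterion in the definition or in the committee's task.

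What remains exposed is the toxicity-form record, mainly of bleeds that do not stop treatment. The documents also do not say which record sends an event to the committee.

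**3. The plan's own monitoring figure (13.4).** For 2 or more events in 25 patients at a true rate of 2%:

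1 − 0.98^25 − 25 × 0.02 × 0.98^24 = 1 − 0.6035 − 0.3079 = 0.0886, which rounds to the stated 0.09.

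It reproduces. It describes Arm B alone; the trigger is a difference between arms of at least 3.

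**4. What the filter could do to the trigger, if the count came from filtered forms.** Inputs:

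- 25 per arm (13.2) and a difference of at least 3 at any point (13.4).
- True rates of 10% in Arm B and 2% in Arm A. These are assumptions; the only rate that 13.4 states is 2%, for Arm B.
- A share q of bleeds dropped as not attributable, equal in both arms. This is an assumption; the documents give no figure.

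Recorded rate = true rate × (1 − q). Patients are taken in 25 pairs. For each pair the difference B − A rises by 1 with probability pB(1 − pA), falls by 1 with probability pA(1 − pB), and otherwise stays. The trigger is reached when the difference first equals 3. At q = 0 the up and down probabilities are 0.10 × 0.98 = 0.098 and 0.02 × 0.90 = 0.018. At q = 50% they are 0.05 × 0.99 = 0.0495 and 0.01 × 0.95 = 0.0095.

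| q | Recorded rate B / A | P(trigger at any point) |
|---|---|---|
| 0 | 10% / 2% | 0.381 |
| 20% | 8% / 1.6% | 0.269 |
| 30% | 7% / 1.4% | 0.213 |
| 50% | 5% / 1% | 0.110 |

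Two variations show the range. With true rates of 8% and 2%, judged only at the end of the trial, the probability is 0.240 with full recording and 0.145, 0.063 and 0.012 with q of 25%, 50% and 75%. With 2% in both arms, at any point, it is 0.009 with full recording and 0.002 at q = 50%.

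**The case against.** The strongest reply is that the bleeds that matter most are already captured elsewhere. Bleeds that stop treatment are documented in the case report form whatever their cause, scheduled visits ask about any bleeding, fatal events are reported regardless of attribution, and severity is decided by a blinded committee. All of this stands. A reader might infer from 7.7 that the primary bleeding rates themselves hang on investigator opinion; the documents do not support that, because neither the endpoint definition nor the analysis in 13.5 uses attribution.

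A reader might also infer that the DSMB sees only filtered bleeding data. That goes too far as well. Section 12.2 is permissive and makes other information available on request. Section 13.4 counts hemorrhages, not attributable adverse events, and promises hemorrhage rates to the DSMB. Nothing ties that count to the toxicity form, but nothing ties it to another source either.

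The loss shares may also be too high. If 7.7 uses the scale in 7.3 and 7.4.1, where a possible relation counts as attributed, a bleed on an anticoagulant is dropped only when the link is thought doubtful or absent. The documents do not show that the cancer is the usual explanation for a bleed in these patients, and 3.2 excludes active bleeding and several high-risk conditions. This is fair: the figures illustrate a mechanism and do not forecast a loss.

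Finally, a reader might suspect bias towards one arm. Physicians and participants are blinded up to the day 14 assessment, so attribution in that period should lower counts in both arms.

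None of this reconciles the two sentences of 7.7 or supplies the missing adverse-event route for non-fatal bleeds.

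**Conclusion.** The contradiction within 7.7, and between 7.7 and 7.1, is plain on the text and rests on no assumption. Followed as written, the attributable-only sentence, together with the filters in 7.4, lets the bleeding adverse-event data be incomplete, mainly for non-fatal bleeds that do not stop treatment. The primary major-hemorrhage endpoint is largely protected.

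The consequence for monitoring is conditional. If the 13.4 count were drawn from attribution-filtered forms, the trigger would lose sensitivity: from 0.38 to 0.11 under assumed true rates of 10% and 2% with half of bleeds dropped, and from 0.38 to 0.27 with a fifth dropped. If the count uses scheduled assessments or adjudicated events that capture every bleed, the loss is nil. The plan should be changed because the ambiguity is real and cheap to remove, not because the primary result is in doubt.

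**What to change.** In 7.7, replace the two conflicting sentences with a rule that every bleeding event of any grade from the first dose is recorded regardless of attribution and sent to the adjudication committee. Attributable-only recording may stay for other adverse events, apart from deaths and thrombotic events, for which the protocol already has capture routes (7.4 and section 11); a cross-reference to these would help.

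In 13.4, state that the between-arm hemorrhage count and the DSMB reports use that complete list.

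The cost is one or two sentences and a few more event forms in 50 patients, each on study for about two weeks. Sample size, endpoints and analysis do not change.
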